3.1 PRIMARY OBJECTIVES

- Evaluate the tolerability and safety of INO-4700 administered by ID injection followed by EP in healthy adult volunteers
- Evaluate the cellular (T cell) and humoral immune response to INO-4700 administered by ID injection followed by EP for identification and confirmation of an optimal dose and regimen
- Evaluate selected optimal dose for safety and immunogenicity

3.2 PRIMARY ENDPOINTS

Safety Endpoints:

- Incidence of adverse events by system organ class (SOC), preferred term (PT), severity and relationship to investigational product
- Administration (i.e., injection) site reactions (described by frequency and severity)
- Incidence of adverse events of special interest

Immunogenicity Endpoints:

- Overall Immune response
 - MERS-CoV antigen specific antibodies
 - Antigen-specific cytokine-producing T cell responses

3.3 EXPLORATORY OBJECTIVE

- Evaluate the expanded immunological profile by assessing both T and B cell immune responses
- Evaluate the cellular (T cell) and humoral immune response to INO-4700 administered by ID injection followed by EP for impact of boosting with a third dose
- Evaluate humoral immune response cross reactivity to other coronaviruses

3.4 EXPLORATORY ENDPOINT

- Expanded immunological profile which may include (but not limited to) additional assessment of T and B cell numbers and T and B cell molecular changes by measuring immunologic proteins and mRNA levels of genes of interest at all weeks as determined by sample availability
- Antibodies to other coronaviruses

3.5 SAFETY ASSESSMENT

For Part 1, adverse events will be collected at every visit and safety samples will be drawn at Screening, Week 2, Week 6, Week 10 and Week 48. For Part 2, adverse events will be collected at every visit and safety samples will be drawn at Screening, Week 2, Week 6 (if optimal regimen includes dosing at Week 4), Week 10 (if optimal regimen includes dosing at Week 8), Week 48, Week 50 (for participants receiving three doses) and Week 68 (for participants receiving three doses). Refer to the Schedule of Events

[Table 4](#), [Table 5](#) and [Table 6](#) for additional details.

For both Parts 1 and 2, all adverse events, regardless of relationship, will be collected from the time of consent until study discharge.

Additionally, for both Parts 1 and 2, a pregnancy test will be performed at screening and prior to each dose.

3.6 IMMUNOGENICITY ASSESSMENT

For Part 1, immunology blood samples will be collected at Screening, Day 0, Week 6, Week 10 and Week 48. For Part 2, immunology blood samples will be collected at Screening, Day 0, Week 6 (if optimal regimen includes dosing at Week 4), Week 8 (if optimal regimen includes dosing at Week 8), Week 10 (if optimal regimen includes dosing at Week 8), Week 12 (if optimal regimen includes dosing at Week 4), Week 48, Week 50 (for Part 2B participants receiving three doses) and Week 68 (for Part 2B participants receiving three doses). Refer to the Schedule of Events [Table 4](#), [Table 5](#) and [Table 6](#) for additional details. Determination of analysis of collected samples for immunological endpoints will be determined on an ongoing basis throughout the study.

4.0 CLINICAL TRIAL POPULATION

4.1 INCLUSION CRITERIA

- a. Able to provide informed consent and have signed Informed Consent Form (ICF) prior to screening procedures;
- b. For Part 1, adults age 18 and 50 years, inclusive. For Part 2, adults at least 18 years of age;
- c. Judged to be healthy by the Investigator on the basis of medical history, physical examination and vital signs performed at Screening. **Note:** Participants taking daily prescription or non-prescription medications for management of acceptable chronic medical conditions must be on a stable dose, as defined by non-change in dose for the 3 months prior to the first dose of study medication and no planned changes during the active dosing period of the study;
- d. Able and willing to comply with all study procedures;
- e. Screening laboratory results within normal limits for testing laboratory or deemed not clinically significant by the Investigator;
- f. Negative serological tests for Hepatitis B surface antigen (HBsAg), Hepatitis C antibody and Human Immunodeficiency Virus (HIV) antibody or rapid test at screening;
- g. Screening ECG deemed by the Investigator as having no clinically significant findings (e.g. Wolff-Parkinson-White syndrome);
- h. Must meet one of the following criteria with respect to reproductive capacity:
 - Women who are post-menopausal as defined by spontaneous amenorrhea for \geq 12 months;
 - Surgically sterile or have a partner who is sterile (i.e., vasectomy in males at least six (6) months prior to enrollment or tubal ligation, absence of ovaries and/or uterus in females);
 - Use of medically effective contraception with a failure rate of $< 1\%$ per year when used consistently and correctly from screening until 3 months following last dose. Acceptable methods include:
 - hormonal contraception including implants, injections or oral;
 - two barrier methods, e.g., condom and cervical cap (with spermicide) or diaphragm (with spermicide);

- abstinence when this is the subject's preferred and usual lifestyle. **Note:** Periodic abstinence (e.g., calendar, ovulation, symptothermal, or post-ovulation methods) and withdrawal are not acceptable methods of contraception.

4.2 EXCLUSION CRITERIA

- a. Pregnant or breastfeeding, or intending to become pregnant or father children within the projected duration of the trial starting with the screening visit until 3 months following last dose;
- b. Positive serum pregnancy test during screening or positive urine pregnancy test prior to dosing;
- c. History of respiratory diseases such as asthma, chronic obstructive pulmonary disease or chronic bronchitis;
- d. Is currently participating in or has participated in a study with an investigational product within 30 days preceding Day 0;
- e. Previous receipt of any vaccine within 30 days preceding Day 0 or planning to receive any vaccine during the timeframe restricted per the protocol;
- f. Previous receipt of an investigational vaccine product for prevention of MERS;
- g. Prior exposure to MERS-CoV or camels (serology or antibody testing will be requested at the Investigator's discretion);
- h. Participants who participated in MERS-201 Part 1 cannot participate in MERS-201 Part 2;
- i. Fewer than two acceptable sites available for ID injection and EP considering the deltoid and anterolateral quadriceps muscles. The following are unacceptable sites:
 - Tattoos, keloids or hypertrophic scars located within 2 cm of intended administration site;
 - Implantable-Cardioverter-defibrillator (ICD) or pacemaker (to prevent a life-threatening arrhythmia) that is located ipsilateral to the deltoid injection site (unless deemed acceptable by a cardiologist);
 - Any metal implants or implantable medical device within the electroporation site;
- j. Prisoner or participants who are compulsorily detained (involuntary incarceration);
- k. Current or anticipated concomitant immunosuppressive therapy (excluding inhaled, topical skin and/or eye drop-containing corticosteroids) prior to dosing. Systemic corticosteroids must be discontinued at least 3 months prior to first dose;
- l. Reported active drug or alcohol or substance abuse or dependence.

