6.4.1 INJECTION AND EP

Participants in Part 1 Study Groups A, B and C will receive one injection of INO-4700 in a volume of ~0.1 mL by ID injection above an acceptable muscle location for injection, the injection site is assessed for IP leakage, and the injection is followed immediately by EP. Part 1 Study Groups D and E will receive two injections of INO-4700, each in a volume of ~0.1 mL, above an acceptable muscle location on two different limbs, the injection site is assessed for IP leakage, and the injection is followed immediately by EP. Part 1 Study Groups F and G will receive one injection of placebo in a volume of ~0.1 mL by ID injection above an acceptable muscle location for injection, the injection site is assessed for IP leakage, and the injection is followed immediately by EP. Part 1 Study Groups H and I will receive two injections of placebo, each in a volume of ~0.1 mL, above an acceptable muscle location on two different limbs, the injection site is assessed for IP leakage, and the injection is followed immediately by EP.

Participants in Part 2 will receive one or two injections per dosing visit of the optimal dose of INO-4700 or placebo in volume of ~0.1 mL by ID injection above an acceptable skin location for injection, the injection site is assessed for IP leakage, and the injections is followed immediately by EP.

Only if the deltoid muscle is not a suitable location (see exclusion criterion 'h'), the ID injection can then be administered above the lateral quadriceps followed immediately by EP. IP must not be given within 2 cm of a tattoo, scar, keloid, previous injection site at the same dosing visit, or active lesion/rash. Also, ID injection followed immediately by EP must not be performed on the skin of an extremity which has any metal implants or implantable medical device (e.g., surgical rods, pins or joint replacements). If a subject has an implanted cardiac defibrillator or pacemaker, ID injection/EP must not be performed above the deltoid muscle on the same side of the body where the device is located.

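### Protocol 4.2 and 6.4.1 give conflicting rules on electroporation near cardiac devices and metal implants, and the cross-reference between them is stale

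*Protocol*

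**What the plan says.** Section 4.2 criterion i, repeated in the Synopsis, excludes a volunteer with "Fewer than two acceptable sites available for ID injection and EP considering the deltoid and anterolateral quadriceps muscles". It then lists what makes a site unacceptable. One item is an ICD or pacemaker "that is located ipsilateral to the deltoid injection site (unless deemed acceptable by a cardiologist". Another is "Any metal implants or implantable medical device within the electroporation site".

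Section 6.4.1 governs administration. For cardiac devices it says that "ID injection/EP must not be performed above the deltoid muscle on the same side of the body where the device is located". For implants it says that injection with electroporation "must not be performed on the skin of an extremity which has any metal implants or implantable medical device", giving rods, pins and joint replacements as examples.

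Section 6.4.1 also lets the injection move to the lateral quadriceps, under a condition that begins "Only if the deltoid muscle is not a suitable location (see exclusion criterion 'h". In v2.0 criterion h reads "Participants who participated in MERS-201 Part 1 cannot participate in MERS-201 Part 2"; the rule on injection sites is criterion i.

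**The concern.** Both texts are current and operative, and they differ on the same physical question. Criterion i is more than a head-count rule, because it defines sites that are acceptable for injection and electroporation. A cardiologist's acceptance has no practical effect unless that deltoid may then be used, and 6.4.1 does not allow it. The rule concerns electrical pulses near implanted devices, so a text that can be read two ways is a safety matter first.

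There is a smaller consequence for the data. Eligibility is settled before assignment (Section 6.1.2), and Part 1 participants are randomised across groups A to I (Section 8.7). Someone can be enrolled by counting a site that 6.4.1 prohibits and then be assigned a regimen needing two limbs. Section 6.0 grants no waivers, and Section 4.3 does not replace those who withdraw. A missed planned administration removes a participant from the per-protocol set (Section 8.4; SAP 2.1), which SAP Section 5 makes the key population for immunogenicity.

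**Working it through.** The plan gives no figure on this point to reproduce. The check is a comparison of the two texts and a count of usable sites.

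**1. The texts side by side (Protocol v2.0)**

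| Situation | Section 4.2, criterion i | Section 6.4.1 |
|---|---|---|
| ICD or pacemaker, same-side deltoid, cardiologist accepts | Acceptable | Prohibited |
| Metal or implanted device in the limb but outside the electroporation site | Acceptable | Prohibited for the whole extremity |
| Metal or implanted device inside the electroporation site | Unacceptable | Prohibited |

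The first two rows conflict and the third agrees. The same conflicts stand in v1.0. Neither the v2.0 summary of changes nor the administrative-memo items in the documents address them.

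**2. One affected arm.** Suppose there is metal elsewhere in an arm. Under 4.2 that deltoid is suitable, so the quadriceps fallback in 6.4.1, which defers to the exclusion criterion, is not triggered. Later in the same paragraph, 6.4.1 bars the arm. Enrolment is unaffected, but two trial centres could reasonably choose different limbs.

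**3. When is someone eligible under 4.2 but short of two permitted sites under 6.4.1?** There are four candidate sites, each on a different limb: two deltoids and two quadriceps.

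*Cardiac device accepted by a cardiologist.* Let k of the other three sites be usable. Section 4.2 counts k + 1 and 6.4.1 counts k.

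| k | Site patterns | Count under 4.2 | Count under 6.4.1 |
|---|---|---|---|
| 0 | 1 | 1 (excluded) | 0 |
| 1 | 3 | 2 (eligible) | 1 |
| 2 | 3 | 3 (eligible) | 2 |
| 3 | 1 | 4 (eligible) | 3 |

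The shortfall arises only at k = 1, which is 3 of the 3 + 3 + 1 = 7 eligible patterns. This counts patterns and is not a probability.

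*Metal outside the electroporation site in m limbs, no other problem.* Section 4.2 counts 4 and 6.4.1 counts 4 − m. Fewer than two remain only when m is 3 or more. If u further sites are lost under both texts, the counts are 4 − u and 4 − u − m, so the threshold falls to m = 2 at u = 1 and m = 1 at u = 2.

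**4. Who would be undoseable.** With one permitted site left, a one-injection group can still be dosed. A two-limb group cannot be dosed without breaching 6.4.1. The two-limb groups are D and E ("Part 1 Study Groups D and E will receive two injections of INO-4700, each in a volume of ~0.1 mL") and placebo groups H and I. Together they number 32 + 32 + 8 + 8 = 80 of 192, or 41.7%. That is the share of Part 1 allocated to two-limb regimens, not the share affected.

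**The case against.** The best defence is that the two sections do different jobs. Criterion i counts sites for eligibility, 6.4.1 controls dosing, and a centre that follows 6.4.1 never breaches 4.2. That last statement is correct, so no centre is forced into a violation. It does not remove the conflict. Criterion i defines acceptability for electroporation itself, 6.4.1 defers to that criterion for deltoid suitability, and no precedence is written down.

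A second defence is that the device User Manual covers contraindications (Section 5.3.2) and centres are trained before first dose (Section 5.6). These may have settled the matter in practice. The manual is not among the documents, so it cannot be assumed to do so.

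The objection on scale stands. A reader might infer broad exposure from the 80 of 192 on two-limb regimens, but almost none of those people need have an implant. A reader might also infer that participants are commonly randomised and then cannot be dosed. Step 3 shows that this needs most candidate sites to be unusable, and participants are randomised to groups, not to injection sites. Cardiac devices should be rare in volunteers aged 18 to 50 who are judged healthy and have no clinically significant ECG finding (Section 4.1); the metal-implant conflict is the more practical one. Finally, the 350 planned for Part 2, with no upper age limit, might suggest a larger problem. The administrative memo on discontinuation says that the trial does not proceed to Part 2.

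**Conclusion.** The contradiction is real and lies in the current text. It has two parts, cardiac devices and metal or other implants, and the stale reference to criterion h adds to it. Its weight is that of an inconsistent safety instruction that is cheap to correct. The documents give no frequency of implants; that affected participants are few is a judgement from the eligibility criteria.

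The data consequence is limited to Part 1. It requires an implant, the loss of most other sites and, chiefly, assignment to group D, E, H or I. No sample size, power, error rate or other stated figure is affected. The documents do not support reading this as a material threat to the per-protocol analysis. Nor do they show that anyone was dosed at a prohibited site.

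**What to change.** Reconcile the Synopsis, Section 4.2 criterion i and Section 6.4.1. One identical statement for cardiac devices, and one for metal and other implantable devices, should define both an acceptable site for eligibility and a permitted site for administration. Change the cross-reference in 6.4.1 from criterion h to criterion i. The sponsor must decide which rule applies; this review takes no view.

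The cost is a clarifying amendment or administrative memo, with no change to the analysis. The discontinuation memo rests on Week 10 results, and Section 8.2 places that review after all Part 1 participants have completed Week 10. Part 1 dosing, at Day 0 and Week 4 or 8, was therefore over by then. A correction made after that point would serve the record and any later protocol that reuses this text.

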4.3 DISCONTINUATION/WITHDRAWAL OF CLINICAL TRIAL PARTICIPANTS

Participants may withdraw consent at any time for any reason or be dropped from the trial at the discretion of the Investigator should any untoward effect occur. In addition, the Investigator or the Sponsor has the right to withdraw a subject from the trial at any time.

The Investigator must notify the Sponsor immediately when a subject has been discontinued/withdrawn due to an Adverse Event (AE). If a subject discontinues from the trial or is withdrawn from the trial prior to trial completion, all applicable activities scheduled for the final trial visit (i.e., Part 1 Week 48 EOS or Part 2 Week 48 or 68 EOS) should be performed at the time of discontinuation. Any AEs and/or Serious Adverse Events (SAEs) present at the time of discontinuation/withdrawal should be followed in accordance with the safety requirements outlined in [Section 7.9: Safety Data Reporting Period, Method of Collection and Submission](#).

Unless a subject refuses to continue participation, all follow-up visits and procedures should be completed as indicated in the Schedule of Events (Tables 3, 4 and 5) following the last dose whether or not the subject has completed all doses.

Reasons for withdrawal from the trial may include but are not limited to the following:

- Subject withdrawal of consent at any time
- Any medical condition that the Investigator or Sponsor determines may jeopardize the subject's safety if he or she continues in the trial
- Investigator, DSMB or Sponsor determines it is in the best interest of the subject
- Subject non-compliance

Every effort should be made to obtain information on participants who withdraw from the trial. The primary reason for withdrawal from the trial should be documented on the appropriate eCRF. However, participants will not be followed for any reason after consent has been withdrawn. Data and/or samples collected prior to withdrawal of consent will be analyzed.

Subject dosing may be discontinued if they experience any of the following:

- Adverse Event (Adverse Reaction)
 - The Investigator or trial coordinator must notify the Sponsor immediately when a subject has been discontinued/withdrawn due to an Adverse Event (AE).
- Any medical condition that may jeopardize the subject's safety if he or she continues on trial
- Pregnancy

Subjects who discontinue or withdrawal from the study will not be replaced.

5.0 CLINICAL TRIAL TREATMENT

5.1 INVESTIGATIONAL PRODUCTS (IPs) AND STUDY DEVICE

5.1.1 INO-4700 AND SSC-0001

Investigational product is defined as a pharmaceutical form of an active ingredient or placebo being tested or used as a reference in the study, whether blinded or unblinded.

INO-4700 is the active investigational product to be used in this study. The INO-4700 drug product contains 10 mg/mL pGX9101 in 1X SSC buffer (150 mM sodium chloride and 15 mM sodium citrate). A volume of 0.4 mL will be filled into 2-mL glass vials that are fitted with rubber stoppers and sealed aluminum caps. INO-4700 must be placed in 2–8°C storage immediately upon arrival and requires preparation prior to administration, which is outlined in the pharmacy manual.

pGX9101 is a DNA plasmid expressing a synthetic consensus (SynCon®) Middle East Respiratory Syndrome Human Coronavirus Spike protein (MERS-CoV Spike), driven by a human CMV promoter (hCMV promoter), and with the bovine growth hormone 3' end poly-adenylation signal (bGH polyA). The pGX0001 backbone includes the kanamycin resistance gene (KanR) and plasmid origin of replication (pUC ori).

Sterile saline sodium citrate (SSC) buffer (SSC-0001), which contains sterile 150 mM sodium chloride and 15 mM sodium citrate in 2-mL or 10-mL glass vials, stoppered, and sealed with aluminum caps, will be used as the placebo at the clinical site.

5.1.2 CELLECTRA™ 2000

The CELLECTRA™ 2000 is a portable, battery-powered medical device designed to generate a minimally-controlled, electric field which temporarily and reversibly increases cellular membrane permeability without damaging the tissue. During the period of increased permeability an indicated injected plasmid DNA formulation can be introduced into the cells.

The CELLECTRA™ 2000 device is indicated to enhance the uptake and expression of DNA plasmid-based biologics in order to enhance vaccine efficacy. The DNA plasmid is delivered separately via needle and syringe injection immediately prior to the electroporation. The electroporation is accomplished through a sterile, disposable needle Array attached to an Applicator delivering current controlled electrical pulses as follows:

- An EP treatment consists of four pulses.
- An Array of three stainless steel electrode needles is used to deliver the electrical pulses into the tissue.
- Voltage levels are limited to 200 volts (V) for patient safety.
- The specified current is constantly maintained through voltage modulation using an analog feedback loop. Measurements of voltage and current are processed for error reporting and collected for data logging.

The CELLECTRA™ 2000 device for ID administration is comprised of three components: (1) A battery-powered Pulse Generator, (2) an ID Applicator that is connected to the pulse generator, and (3) a three-point sterile disposable ID Array of stainless steel needles.

5.2 TREATMENT REGIMENS

- Part 1 Group A – One 0.6 mg ID injection of INO-4700 followed by EP administered at Day 0 and Week 4 (\pm 5 days)
- Part 1 Group B – One 1.0 mg ID injection of INO-4700 followed by EP administered at Day 0 and Week 4 (\pm 5 days)
- Part 1 Group C – One 1.0 mg ID injection of INO-4700 followed by EP administered at Day 0 and Week 8 (\pm 5 days)
- Part 1 Group D – Two 0.5 mg ID injections (in an acceptable location on two different limbs) of INO-4700 followed by EP administered at Day 0 and Week 8 (\pm 5 days)
- Part 1 Group E – Two 1.0 mg ID injections (in an acceptable location on two different limbs) of INO-4700 followed by EP administered at Day 0 and Week 4 (\pm 5 days)
- Part 1 Group F – One ID injection of placebo followed by EP administered at Day 0 and Week 4 (\pm 5 days)
- Part 1 Group G – One ID injection of placebo followed by EP administered at Day 0 and Week 8 (\pm 5 days)
- Part 1 Group H – Two ID injections (in an acceptable location on two different limbs) of placebo followed by EP administered at Day 0 and Week 8 (\pm 5 days)
- Part 1 Group I – Two ID injections (in an acceptable location on two different limbs) of placebo followed by EP administered at Day 0 and Week 4 (\pm 5 days)
- Part 2 – Dose and regimen to be determined, each ID injection(s) followed by EP administered at Day 0, Week 4 or Week 8, and Week 48 (for Part 2B participants receiving a third dose)

INO-4700 or placebo will be administered intradermally in ~0.1 mL dose volume followed immediately by EP.

